- ICU length of stay (LOS)
- Hospital LOS
- End organ failure (measured by BUN, creatinine, and liver function tests)

The secondary study endpoints are to evaluate whether NO delivered through the neonatal CPB circuit can decrease various biochemical markers of ischemia/reperfusion injury and oxidative damage. Markers to be analyzed will include:

- cardiac troponin I
- N-terminal prohormone for brain natriuretic peptide (NT-proBNP)
- plasma malondialdehyde (MDA) levels
- superoxide dismutase
- interleukins (IL)
- lactate dehydrogenase (LDH)
- procalcitonin
- tumor necrosis factor (TNF alpha)
- C-reactive protein (CRP)
- Creatine phosphokinase-MB (CPK-MB)

The primary safety measure is the level of methemoglobin while NO is being administered during cardiopulmonary bypass. The level will be checked every

½ hour per standard clinical practice, and NO administration will be adjusted accordingly, to keep the methemoglobin level below 3%.

10) Procedures Involved

Design

The study will employ a double-blind placebo-controlled randomized block design.

Sample

Twenty-four neonates with HLHS or its variants requiring surgical repair in the first few days of life will be randomized into 2 groups.

Group 1 will include 12 subjects who will receive inhaled NO via the CPB circuit for the duration of surgery. Group 2 will include 12 control subjects. These controls will receive an identical NO via CPB set-up, but will not receive NO during surgery. The subjects in both groups will undergo the standard Norwood procedure with a central systemic to pulmonary shunt or right ventricle to pulmonary artery shunt (Sano shunt). The only difference between groups will be the administration of NO via CPB.

Standard Intra-operative protocol:

After induction of general anesthesia using opiates (Fentanyl) and muscle relaxant, appropriate arterial line and central venous line access will be obtained. Intra-operative monitoring of arterial blood pressure, central venous pressure, systemic oxygen saturation, cerebral and somatic (kidney) near-infrared spectroscopy, will be done throughout surgery.

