After adequate positioning, a regular median sternotomy incision will be done. The thymus gland is resected for better exposure. Under full heparinization (activated clotting time >300 sec), CPB is instituted using an arterial cannula inserted in the ascending aorta (or ductus arteriosus in patients with HLHS), and a venous cannula inserted in the right atrium or 2 separate superior and inferior vena cava cannulas.

Once on CPB, the patient's temperature is cooled down to 28 degrees Celsius. Cooling and warming the patient are done with pH stat strategy, during which the carbon dioxide level is allowed to rise in the CPB circuit to maintain a normal temperature corrected pH. All patients receive inhaled NO through the endotracheal tube after weaning from CPB.

Research procedures

The subjects will be randomized by the research perfusionist to either groups of the study. Only the perfusionist will be aware of the randomization process and NO delivery. The surgeon will be blinded to group assignment. Group 1 (treatment group) will receive NO via the CPB for the duration of surgery. Once the patient is off CPB, NO administration via CPB will be discontinued and switched to endotracheal tube administration. Group 2 (control group) will be treated with a strategy identical to that in the treatment group, with the exception that they will not receive NO via CPB.

For subjects in Group 1, NO will be delivered using the Inovent Transport delivery device (Ikaria, Hampton, NJ) after calibrating the machine according to the manufacturer's instruction. While setting up and priming the CPB circuit, the NO delivery tubing will be incorporated into the oxygenator inlet gas tubing using special reducing connectors. NO sampling will be performed by adding a luer lock connector to the inlet gas tubing proximal to the oxygenator and attaching the sampling line to it.

Once CPB is initiated, NO delivery will be started at 40ppm as measured by the sampling line, and maintained at 40ppm during the procedure unless the serum methemoglobin level increases above 3%. Once the patient is off CPB, NO delivery will be discontinued, and the subject will be managed similar to controls.

Post-surgical care

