The data will be collected and saved on a password-protected Excel data sheet which will be stored on the password-protected computer of principal investigator.

12) Data Management

Sample Size Estimation

Sample size estimation was calculated using PASS 12 (15) based on the number of subjects needed to compare the difference in fluid balance as measured by the total amount of fluid administered in the first 24 and 48 hours for the two groups. Power analysis was run based on published data that showed a difference 130 mL between similar group assignments. (14) A sample size of 12 achieves 83% power to detect a mean difference of 75 mL with an estimated standard deviation of 60 mL and with a significance level (alpha) of 0.05 using a two sample t-test.

Data Management

Standard of care lab values and clinical indicators as identified in protocol Section 9 will be recorded in the electronic medical record (EMR) per routine hospital procedure. Lab values of markers being collected for research only will be received in a report directly from the labs. Investigators will extract study data from the EMR or lab results onto a source document for data collection and record into an electronic spreadsheet.

Statistical Analysis Plan

Data analysis will include measures of central tendency for all demographic and outcome variables. The primary endpoint of clinical indicators, including fluid balance, inotropic support, ventilator hours, and LOS will be compared between groups using a Repeated Measures ANOVA with post hoc comparisons, Student's t-test or chi-square as appropriate. A p-value less than, or equal to, 0.05 will be regarded statistically significant.

Secondary outcomes to be compared between groups include the biochemical markers. Analysis will be done using Student's t-test and a p-value less than, or equal to, 0.05 will be regarded statistically significant.

The other indicators, number of adverse events (as determined by methemoglobin) will also be described and reported as indicated in protocol Section 13. Differences in adverse event rates will be evaluated using descriptive and inferential statistics as appropriate.

Data Storage

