 - [name], MA - Clinical Coordinator, Pediatrics and Pediatric Critical Care, Advocate Children's Hospital-Oak Lawn

- [name] – Pediatric Pulmonologist, Torero Pulmonary Specialists, S.C.

14) Withdrawal of Subjects

The FISH test to test for chromosomal abnormality is done routinely on all neonates with cardiac disease. If the FISH test result is abnormal after the Norwood procedure is performed, indicating genetic syndromes, the subject will be withdrawn from the study.

It may be possible that RV wall and endocardial fibroelastosis may not be evident on the pre-operative echo but that it would be identified during the operation. If this condition is identified during the operation, the subject will be withdrawn at that time, randomization will be unblended and the subject will be treated as if they are not in the study (e.g. will not have extra study blood drawn).

At any time, the attending physician can withdraw a patient from this study if they feel it is warranted based on clinical condition. Parents will be notified by the attending physician. The parents have the right to withdraw their child from the study at any time. If the parent decides to withdraw their child from the study, they will be asked if medical record collection can continue until the end of hospitalization. Documentation of the conversation and their decision will be entered into the research chart and medical record.

15) Risks to Subjects

We have been using *inhaled* NO during and after surgery at our center for over 8 years. The direct risk of using NO in the CPB circuit during surgery is related to elevated methemoglobin serum level. An elevated methemoglobin level is usually treated effectively by decreasing the rate of NO administration. All surgical staff and team members are familiar with NO use.

NO administration via the cardiopulmonary bypass circuit will be monitored by checking frequent methemoglobin levels. Per our standard practice, this level is checked with every arterial blood gas which is usually performed every 30 minutes while the patient is on cardiopulmonary bypass. If the methemoglobin level increases to 3%, NO administration will be decreased until methemoglobin falls below this level. No other research-related risks are anticipated.

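### The NO dosing threshold conflicts between sections at a methemoglobin reading of exactly 3%, and the primary safety measure as worded leaves out the controls

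*Combined protocol and SAP*

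**What the plan says.** Three places govern the NO dose in the bypass circuit.

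- Section 9 (Study Endpoints) gives the aim: "NO administration will be adjusted accordingly, to keep the methemoglobin level below 3" percent.
- Section 10 (Procedures Involved, Research procedures) gives the delivery instruction. NO starts at 40 ppm when bypass begins and is "maintained at 40ppm during the procedure unless the serum methemoglobin level increases above 3" percent.
- Section 15 (Risks to Subjects) gives the response: "If the methemoglobin level increases to 3%, NO administration will be decreased until methemoglobin falls below this level".

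Section 9 also sets the safety measure: "The primary safety measure is the level of methemoglobin while NO is being administered during cardiopulmonary bypass". Under Section 10, controls have the same circuit set-up but no NO through it. Inhaled NO by endotracheal tube is given to all infants, but only after weaning from bypass.

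On measurement, Section 15 says that as standard practice "this level is checked with every arterial blood gas which is usually performed every 30 minutes while the patient is on cardiopulmonary bypass". On analysis, the Statistical Analysis Plan in Section 12 says that the "number of adverse events (as determined by methemoglobin) will also be described and reported as indicated in protocol Section 13". Its next sentence reads: "Differences in adverse event rates will be evaluated using descriptive and inferential statistics as appropriate".

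**The concern.** Section 15 names raised methemoglobin as the direct risk of giving NO through the circuit, and Section 32 says this is the first such use at the institution. The perfusionist, who alone knows the allocation, needs a single trigger for lowering the dose in a neonate. The less cautious version stands in the procedures section, which is the one most likely to be followed in the operating room.

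The second issue is the population covered by the primary safety measure. A measure confined to time on circuit NO has no value for an infant who never receives it. Methemoglobin on bypass without NO is the natural reference for the treated arm, and the wording sets it aside although the readings should already exist.

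**Working it through.** The plan attaches no computed figure to this point, so the check is a comparison of text.

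**Dosing rule.** Each section applied to the three possible cases:

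| Reading | Section 9 | Section 10 | Section 15 |
|---|---|---|---|
| Below 3% | aim met | stay at 40 ppm | no reduction |
| Exactly 3% | aim not met, adjust | stay at 40 ppm | reduce |
| Above 3% | adjust | 40 ppm no longer held | reduce |

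The sections agree in the first and third rows. In the middle row Section 10 stands alone against the other two.

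**Size of the dosing conflict.** With a gas about every 30 minutes, following Section 10 at a reading of 3% keeps the infant at 40 ppm until the next gas. Section 15 would have lowered the dose at once, to some level r ppm. For bypass time T minutes, the extra exposure from that one reading, as a share of full-dose exposure, is

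(40 − r) × 30 / (40 × T).

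The documents give neither r (Section 15 says only that NO is decreased) nor T, so no percentage follows. How often a reading falls on exactly 3% depends on how the analyser rounds, which is also not stated.

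**Safety measure.**

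1. Section 9 limits the measure to time on NO during bypass.
2. Section 10 gives controls no NO during bypass. Their later inhaled NO falls outside that window.
3. As worded, up to 12 treated infants contribute and 0 of 12 controls do.
4. Section 15 describes the methemoglobin check as standard practice with every arterial gas on bypass and does not confine it to treated infants. Section 12 (Data Management) has the standard of care values named in Section 9 entered in the medical record. Control readings should therefore exist.
5. Section 10's list of clinical data to be collected does not name methemoglobin. However, the Schedule of Events table and the data collection form (Attachment E) are not in the readable text, so nothing can be concluded about what is recorded.

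**The case against.** The strongest reply is that both faults are narrow. Two of the three sections already agree on the cautious rule, all three agree above 3%, and no harm is shown from staying at exactly 3% for one more gas interval. This stands, and it is why the point is minor. It does not remove the contradiction.

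On the safety measure, the reply is that Section 9 describes exposure monitoring. The sentence is followed at once by the half-hourly check and the dose adjustment, which can only concern infants on NO. That is a fair reading of the intent. It leaves open whether the control readings belong to the protocol's primary safety measure.

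Three stronger conclusions might be drawn, and the documents support none of them.

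- A reader might infer that a planned between-arm comparison has an empty control arm. That is one reading of Section 12. The sentence on differences in rates can equally refer to general adverse events, which Section 13 collects in all infants and compares between groups.
- A reader might infer that control data will be missing. The routine gases point the other way.
- A reader might treat 30 minutes divided by an assumed bypass time as the share of NO exposure at stake. That is a share of time. It equals a share of exposure only if NO is stopped, and Section 15 has it decreased.

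The low power of any event comparison at 12 against 12 is a property of the trial's size. The wording does not cause it, and the fix does not change it.

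**Conclusion.** The point holds as a minor internal inconsistency. The dosing threshold is contradictory at a reading of exactly 3%, with an effect of about one 30-minute interval per such reading and an exposure difference that cannot be calculated from the documents. Separately, the primary safety measure literally covers only the 12 treated infants. That is a wording fault; it does not show a gap in the data. The missing methemoglobin cut-off for an event, and the unstated choice among repeated readings, are mostly missing detail.

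The conclusion on dosing rests on the text alone. The conclusion on the safety measure assumes that the standard practice in Section 15 applies to both arms, as its wording suggests. Neither part touches the sample size or the efficacy analysis.

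**What to change.** 1. In Section 10, hold 40 ppm *unless the methemoglobin level reaches 3% or more*. This matches Sections 9 and 15.
2. In Section 9, define the primary safety measure as peak methemoglobin during bypass in both arms, taken from the routine arterial gases. In Section 12, summarise it by arm.
3. If readings of 3% or more are also to be counted as events, say so, and specify who sees them. Such a reading would suggest allocation to NO. The PI is one of the operating surgeons (Section 22), surgeons are to be blinded (Section 10), and Section 13 makes the PI responsible for safety monitoring, with adverse events reviewed individually. The perfusionist should therefore hold these readings and pass them to the DSMB, and the PI should not receive them until unblinding. The route exists, since Section 13 already has the perfusionists give the DSMB the randomization code. An event that meets the seriousness criteria would still follow the reporting rules in Section 13.

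The first two changes are wording only and need no extra blood or tests. The third adds a small handling step, which is the downside. Section 12 already carries some of this unblinding risk by counting methemoglobin events, but a defined event would make it more explicit.

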- Preoperative sepsis
- Renal dysfunction, (preoperative creatinine greater than 1.0)
- Intracranial hemorrhage (preoperative intraventricular hemorrhage more or equal to grade 1)
- Known Chromosomal abnormalities and/or known genetic syndromes. (The Fluorescent in situ hybridization (FISH) test is routinely done on all neonates with cardiac disease. If the test results are not received before surgery, the subject will be withdrawn as indicated in protocol section 14.)
- Prior cardiac intervention, catheter-based or surgical
- RV wall and endocardial fibroelastosis (as determined by pre-operative echocardiography).

6) Study-Wide Number of Subjects

We will enroll a total of 24 subjects with 12 subjects in the treatment group and 12 subjects in the control group.

7) Study-Wide Recruitment Methods

The study will be performed at ACH-OL. The pediatric cardiac surgery division performs approximately 400 surgeries each year at this site. Twenty-four neonates with HLHS or its variants requiring surgical repair in the first few days of life will be randomized into 2 groups.

All newborns with diagnosis of HLHS or its variant, who undergo Norwood procedure and satisfy the inclusion criteria will be invited to participate in the study. Most of these patients are diagnosed prenatally by fetal echocardiography and are born at ACH-OL. Few patients with no prenatal diagnosis or who are born at an outside institution are transferred to ACH-OL for further management. Parents will

be informed about the study by our team of Pediatric Cardiac surgeons when they see the child for a clinical preoperative exam. This exam typically occurs after the child is born and the diagnosis is confirmed by echocardiography, and before the scheduled surgical procedure.

8) Study Timelines

The estimated duration needed to recruit the 24 subjects for the study is around 2 years. Each subject will be enrolled in the study from the time of surgery (Norwood procedure) until discharge. After all the subjects have been enrolled and the data has been collected, we anticipate that 2 to 3 months to finish analyzing the data and write the manuscript.

9) Study Endpoints

The primary study endpoints are to evaluate whether NO delivered through the neonatal CPB circuit can decrease the clinical signs of ischemia/reperfusion injury and/or cardiac dysfunction. Clinical parameters include:

- fluid balance
- diuretics requirement
- inotropic support
- duration of mechanical ventilation (hours)

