After finishing surgery, all subjects will recover in the Pediatric Surgical Heart Unit (PSHU) under the direct care of the pediatric cardiac intensivist and the surgical team. Neither physician nor nurse involved in the post-operative care will be aware of the subject's randomization assignment.

Data collection (see schedule of events below)

All patients will have the following pre-operative labs drawn before surgery as part of our standard of care: complete blood count (CBC), complete metabolic panel, coagulation profile, and blood type and cross match.

On the day of surgery, the following research related markers will be drawn in the operating room after the patient is under anesthesia and after insertion of arterial and central venous access (Time 0): cardiac troponin I, NT pro-BNP, plasma (MDA) level, superoxide dismutase, IL-6, IL-8, lactate dehydrogenase (LDH), procalcitonin, TNF alpha, CRP and CPK-MB. These markers will be rechecked at the end of CPB and before modified ultrafiltration (Time 1), after modified ultrafiltration (Time 2), 12 hours (+/- one hour) after CPB (Time 3) and 24 hours (+/- one hour) after CPB (in the PSHU) (Time 4). The amount of blood needed for each research blood draw will be 2 ml for a total of 10 ml of blood to be drawn for research purposes.

All patients will have an echocardiogram, chest radiography and the following blood tests drawn in the PSHU on a daily basis that includes: complete blood count (CBC), complete metabolic panel with kidney function and liver function tests, and coagulation profile. These tests are conducted as part of our standard of care.

All standard of care laboratory tests will be performed and billed in accordance with usual hospital procedures. All research only labs will be shipped in batch to Immunetech labs and processed according to the appropriate procedures.

Clinical data that will be collected will include: CPB time and aortic cross clamp time, fluid requirements, diuretic requirement inotropic support, ventilator hours, need to leave sternum open, ICU LOS and total hospital LOS, transfusions, blood and coagulation

factors, total amount of chest tube drainage, post-operative complications like bleeding, infection or seizures, renal dysfunction, arrhythmias, and post-operative need for extracorporeal membrane oxygenation (ECMO) support.

Schedule of Events

SOC=standard of care, MUF = modified ultrafiltration

11) Data and Specimen Banking

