After the surgery, subjects will be monitored for any adverse events throughout the course of their hospitalization as outlined in safety monitoring plan protocol (Section 13). Appropriate medical care will be provided for any adverse events.

16) Potential Benefits to Subjects

There are no guaranteed benefits to any subjects in this study. The results of this study will be used to enhance our understanding of the effectiveness of NO to potentially decrease ischemia reperfusion injury that can complicate the surgical procedure and postoperative recovery and may benefit future patients. Potential benefits to the subject could include decreased ischemia/reperfusion injury and systemic inflammatory reaction that is commonly seen after neonatal cardiac surgery. This will be reflected by improved post-operative myocardial function and preserved end organ function (kidney, lung, liver), shorter intensive care unit and hospital stay and improved mortality and morbidity.

17) Vulnerable Populations

This research involves children as a vulnerable population. Informed consent/parental permission will be assured by offering parents multiple opportunities to ask and have their questions answered about the study before enrollment and throughout the study time period. Informed consent/parental permission documentation will be completed as discussed in Section 30. Subjects will be too young to provide assent as they will all be neonates.

18) Multi-Site Research

The study will be performed exclusively at ACH-OL.

19) Community-Based Participatory Research

Not applicable

20) **Sharing of Results with Subjects**

The results of some tests routinely performed as standard of care (including lab values) may be shared with the family by the physician involved in the care. No further sharing of research-only procedures or data will be provided to subjects or their families.

21) Setting

The research will be conducted at ACH-OL with the research interaction taking place in the operating room and post-surgical data collection occurring while subjects are cared for in the PSHU.

22) Resources Available

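### End organ failure, a primary endpoint, has no stated day, window, summary or baseline term; its described post-operative tests are daily PSHU draws, so some natural summaries would depend on ICU stay

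*Combined protocol and SAP*

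**What the plan says.** - **Endpoint.** Section 9 puts "End organ failure (measured by BUN, creatinine, and liver function tests") under the primary endpoints. It gives no threshold, day, window or summary such as peak, mean or change. The same list contains "ICU length of stay (LOS").
- **Post-operative values.** Section 10 (Data collection) describes "the following blood tests drawn in the PSHU on a daily basis that includes: complete blood count (CBC), complete metabolic panel with kidney function"; the same panel covers the liver. It sets no number of days. Section 21 describes "post-surgical data collection occurring while subjects are cared for in the PSHU".
- **Follow-up.** Section 8 states: "Each subject will be enrolled in the study from the time of surgery (Norwood procedure) until discharge". That is longer than the PSHU stay.
- **Pre-operative values.** Section 10 states: "All patients will have the following pre-operative labs drawn before surgery as part of our standard of care"; the list includes a complete metabolic panel. Section 4 excludes "Renal dysfunction, (preoperative creatinine greater than 1.0"), and sets no matching limit for BUN or liver tests.
- **Analysis.** The Statistical Analysis Plan in Section 12 names fluid balance, inotropic support, ventilator hours and LOS, to be compared by repeated measures ANOVA, t-test or chi-square as appropriate. It does not name end organ failure and has no baseline term.
- **Contrast.** Other variables do have fixed times. The research markers are drawn at Times 0 to 4, including one before bypass, and the sample-size text uses fluid given in the first 24 and 48 hours.

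**The concern.** Injury to lower-body organs from the interruption of flow is part of the specific objective in Section 2, and this endpoint is how the trial would show it clinically. If one value is available per PSHU day, an infant who stays longer has more chances to record a high one. ICU stay is determined after randomisation and NO is hypothesised to shorten it, so randomisation does not equalise the observation period. A peak, an ever-abnormal flag or a count of abnormal days would then partly re-measure ICU stay. A repeated measures ANOVA over all PSHU days would lose infants who leave early and, at later days, compare mainly the sickest. Death also cuts the period short.

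Separately, infants come to surgery with different organ function. The panel that records it is already drawn on all of them, but no analysis uses it. With 24 infants, that gives up precision the trial could have at almost no cost.

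**Working it through.** **1. The plan's own figure.** Inputs from Section 12: 12 per group, difference 75 mL, SD 60 mL, alpha 0.05, two-sample t-test. The noncentrality is 75 / (60 × √(2/12)) = 75 / 24.5 = 3.06 on 22 degrees of freedom. Two-sided power is 83.3%, which reproduces the stated 83%. It concerns fluid balance only; the documents give no power for end organ failure.

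**2. Why the number of draws matters.** For k independent daily values with SD s around a flat course, the expected maximum lies above the infant's mean by 1.16s (k = 5), 1.54s (k = 10) and 1.87s (k = 20). The gap between 10 and 20 draws is 1.87s − 1.54s = 0.33s, with no true difference. With lag-1 correlation 0.7 the gap is 0.39s, so autocorrelation alone does not remove it.

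**3. Effect on the test.** The documents give no stay lengths, so these are assumed. The simulation used 12 per arm, the same laboratory process in both arms (flat course, lag-1 correlation 0.7), gamma-distributed stays, each infant's peak, and a two-sided t-test at 0.05.

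| Assumed mean stay, days | Mean difference in peak (SD) | False-positive rate, PSHU-stay window | False-positive rate, fixed 3 draws |
|---|---|---|---|
| 14 vs 14 | 0.01 | 5.2% | 4.9% |
| 14 vs 10 | 0.19 | 8.7% | 5.1% |
| 14 vs 7 | 0.39 | 18.6% | 5.1% |
| 20 vs 10 | 0.39 | 20.3% | 5.1% |

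**4. Sensitivity to the time course.** If values rise early and decay over about 3 days, the peak is usually reached before stays diverge. The gap between 10 and 20 draws then falls to 0.06s-0.10s for an assumed rise of 2s, and to 0.01s-0.02s for 3s. The rates in step 3 are therefore towards the unfavourable end.

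**5. The pre-operative value.** With 12 per arm, the standard error of a chance baseline difference is √(2/12) = 0.41 SD, a 95% range of ±1.96 × 0.41 = ±0.80 SD. The probability that it exceeds 0.5 SD in either direction is 22%. Adjustment leaves a fraction 1 − r² of the residual variance, where r is the correlation between pre- and post-operative values (assumed):

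| r | Variance removed, r² | Equivalent sample size, 1/(1 − r²) | Expected shift from a 0.5 SD imbalance | Unadjusted error given that imbalance |
|---|---|---|---|---|
| 0.3 | 9% | 1.10 | 0.15 SD | 5.4% |
| 0.5 | 25% | 1.33 | 0.25 SD | 6.1% |
| 0.7 | 49% | 1.96 | 0.35 SD | 6.4% |

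Averaged over all randomisations, the unadjusted t-test keeps its level (4.8% to 5.0% simulated).

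**The case against.** The strongest reply is that the window problem belongs to an analysis the plan does not contain. A reader might infer that, as planned, a shorter ICU stay would by itself appear as less organ failure. The documents do not support that: no peak, ever-abnormal or all-PSHU-days summary is specified, and a value on a fixed early day, or a change from baseline, fits the same text and has no such problem. This stands. The defect is an undefined endpoint that leaves the vulnerable summaries open.

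A reader might also infer that values are taken only in the PSHU. Sections 10 and 21 point that way but do not say so. Participation runs to discharge, Section 12 extracts standard-of-care results from the medical record, and Section 10 separately collects post-operative renal dysfunction without limiting it to the PSHU. The schedule of events table is not visible and the data collection form (Attachment E) is not included; either might set the laboratory days.

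On baseline, a reader might infer that pre-existing differences would be counted as reperfusion injury, or that the pre-operative panel is ignored. Neither follows. Allocation is randomised, so baseline differences arise by chance and the overall error rate stays near 5%. Pre-operative creatinine is used for eligibility, and the SAP is silent on baseline adjustment without ruling it out. One narrower point survives: an absolute post-operative threshold would also count an infant whose BUN or liver tests were already abnormal.

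Finally, the sizes rest on assumed stays, time course and correlations. That is so, and the early-peak case shrinks the window effect considerably.

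**Conclusion.** The point holds as a gap in specification with two consequences. First, the visible text lets this primary endpoint be summarised in ways whose observation period depends on ICU stay, another primary endpoint. If a peak over the PSHU stay were used, values followed a flat course and mean stays differed by 4 to 10 days, the false-positive rate would be about 9-20% against a nominal 5%. It would be less if values peak early, and a fixed common window keeps it at 5%. Second, making no use of the pre-operative panel forgoes 9%, 25% or 49% of residual variance at correlations of 0.3, 0.5 or 0.7, and leaves uncorrected a chance imbalance that exceeds 0.5 SD with probability 22%. This second consequence is lost precision, not systematic bias. No figure stated in the plan changes.

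**What to change.** In Section 9, define one variable for each organ-function test over a fixed early post-operative window that is the same for every infant. The sponsor should choose the window within the period when all infants are expected still to be in the PSHU, and state how an infant who leaves the PSHU or dies inside it is handled. In Section 12, name this endpoint and compare arms by ANCOVA with the pre-operative value as covariate. Report later values descriptively. If the schedule of events or Attachment E already fixes the laboratory days, bring that definition into Sections 9 and 12. The exact days, the summary and any log transformation are for the sponsor, provided they are fixed before unblinding.

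The cost is mainly wording, because the values are standard-of-care results; an infant who leaves the PSHU inside the window needs either a further draw or the stated rule. The covariate takes one degree of freedom (22 to 21). The real downside is that injury first appearing after the window is only descriptive.
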